9.2 MEASUREMENT OF TREATMENT COMPLIANCE

Dosing compliance for a specified period is defined as the number of capsules actually taken by a patient during that period divided by the number of capsules prescribed for the same period multiplied by 100. The total number of capsules actually taken during a specific time period will be calculated from the study medication records. The number of capsules expected to be taken for a specific treatment period will be calculated by multiplying the number of days in that period by the number of capsules prescribed to be taken per day.

Descriptive statistics for investigational product compliance during the double-blind treatment period will be presented by treatment group for each period between 2 consecutive visits, as well as for the whole double-blind treatment period, for the Safety Population.

10.0 EFFICACY ANALYSES

The efficacy analyses will be based on the ITT Population. *Baseline* for efficacy is defined as the last non-missing efficacy assessment recorded at or prior to first dose of investigational product. All statistical tests will be 2-sided hypothesis tests performed at the 5% level of significance for main effects. All confidence intervals will be 2-sided 95% confidence intervals, unless stated otherwise.

For efficacy analyses in which study center is a factor, a small center will be defined as a center with fewer than 2 patients in any treatment group in the ITT Population. Small centers will be pooled to form pseudo-centers so that each treatment group includes at least 2 ITT patients within the center. Pooling will be done using the following algorithm:

Based on the number of ITT patients, small centers will be ordered from the largest to the smallest, and centers of the same size will be ordered from the largest center code to the smallest center code. The pooling process starts with the largest small center from the top, hich will be pooled with the smallest from the bottom until a non-small pseudo center is formed. The process will be repeated using the small centers left out after the first pass. If any centers are left out at the end of the process, they will be pooled with the smallest pseudo center. If there is more than 1 smallest pseudo center, the pseudo center with the smallest center code will be selected. In case that the pseudo center formed by pooling all small centers is still a small center, it will be pooled with the smallest non-small center. If there is more than 1 smallest non-small center, the one with the smallest center code will be selected.

These pseudo-centers will be used for all efficacy analyses when the model is adjusted for study center.

By-visit analyses based on the mixed-effects model for repeated measures (MMRM) using the observed case (OC) approach will be performed for all continuous efficacy parameters with multiple post-baseline measurements.

In addition, by-visit analyses using the last-observation-carried-forward (LOCF) approach will be presented for all efficacy parameters. For the LOCF approach, only the postbaseline total score of a parameter will be imputed; individual item scores will not be carried forward to derive the total score. Baseline total score will be carried forward only for the intermittent missing scores immediately after baseline. If all the postbaseline values are missing, the baseline value will not be carried forward.

10.1 PRIMARY EFFICACY PARAMETER(S)

The primary efficacy parameter will be the change from baseline in CDRS-R total score at Week 8. The primary analysis for comparing levomilnacipran vs. placebo for the primary efficacy parameter will be performed using an MMRM with treatment group,

pooled study center, visit, and treatment group-by-visit interaction as fixed effects and the baseline value and baseline value-by-visit interaction as covariates. An unstructured covariance matrix will be used to model the covariance of within-patient scores. The Kenward-Roger approximation (Kenward and Roger, 1997) will be used to estimate denominator degrees of freedom. This analysis will only use the observed cases of postbaseline scores without imputation of missing values. In the event of non-convergence of the model using unstructured covariance matrix, a structured covariance matrix will be used in combination with empirical variance estimate (i.e. sandwich estimator) to address the potential mis-specified situation. The following sequence of alternative covariance structures (First-order antedependence [ANTE (1)], Toeplitz [TOEP], First-order autoregressive [AR(1)] and compound symmetry[CS]) will be considered in the MMRM until convergence.

To control the overall type I error rate for the multiple comparisons across the primary and the secondary hypotheses, a fixed sequence procedure will be applied. Details are provided in Section 10.2.

In addition, two sensitivity analyses, LOCF and pattern-mixture model approaches, will be performed on the primary efficacy parameter.

The LOCF approach is based on an analysis-of-covariance (ANCOVA) model including treatment group and pooled study center as factors and baseline CDRS-R total score as a covariate. The pattern-mixture model approach is based on the non-future dependent missing value restrictions (Kenward et al., 2003) and is performed to assess the robustness of the primary MMRM results to the possible violation of the missing-atrandom assumption. The pattern for the pattern-mixture model will be defined by the patient's last visit with an observed value. The observed CSRS-R total score at a visit is assumed to have a linear relationship with the patient's prior measurements. The missing values will be imputed under the assumption that the distribution of the missing observations differs from that of the observed only by a shift parameter value Δ . The dataset with all missing values imputed will be analyzed using an ANCOVA model with treatment group and pooled study center as factors and baseline CDRS-R total score as a covariate for between-treatment group comparisons at Week 8. The imputation of missing values and the analysis will be performed multiple times and the inference of this sensitivity analysis will be based on the combined estimates using the standard multiple imputation technique. The range of values for the shift parameter Δ is selected as 0 to 6 based on experience with historical data. Technical details of the proposed patternmixture model approach (e.g., the models for the pattern-specific identifiable densities and the unidentified conditional distributions, the shift parameter Δ , and the multiple imputation algorithm) are provided in Appendix I to this SAP.

Graphical display of treatment difference vs. placebo (mean difference \pm SE) in primary efficacy parameter will be provided by pooled study center to examine the consistency of the primary efficacy results across study centers.

The site 0070 ceased operations on October 31, 2020, due to the damage caused by Hurricanes Laura and Delta, which made landfall on August 27, 2020 and October 10, 2020, respectively. One more sensitivity analysis excluding all data from this site will be performed on the primary efficacy parameter. The same MMRM would be applied on all OC of change from baseline to Week 8 in CDRS-R total score except all values of Site 0070.

10.2 SECONDARY EFFICACY PARAMETER(S)

The secondary efficacy parameter is the change from baseline to Week 8 in CGI-S score, which will be analyzed using the MMRM approach similar to the one used for the primary efficacy parameter. A sensitivity analysis will also be performed using the LOCF approach as described in Section 10.1.

To control the overall family-wise type I error rate for multiple comparisons across the primary and the secondary efficacy parameters, the fixed sequence testing procedure will be implemented, i.e., the efficacy analysis of the secondary efficacy parameter will be carried out inferentially only if the null hypothesis for the primary efficacy parameter is rejected.

10.3 ADDITIONAL EFFICACY PARAMETER(S)

The additional efficacy parameters will include the following at each postbaseline visit:

- CGI-I score
- Change from baseline in CGI-S score
- CDRS-R response (≥ 40% reduction in CDRS-R from baseline) rate
- CDRS-R remission (CDRS-R \leq 28) rate

The CGI-I score and change from baseline in CGI-S score will be analyzed using the MMRM and the LOCF approaches similar to the ones used for the primary efficacy parameter. For the analysis of CGI-I score, the baseline CGI-S score will be used as the baseline variable.

The CDRS-R response rate and CDRS-R remission rate will be analyzed using a generalized linear mixed model (GLMM), based on a logit link function, with a random intercept and fixed effect terms of treatment group, visit, treatment-by-visit interaction, and baseline score. If the GLMM does not converge, a logistic regression model with treatment group and baseline score as explanatory variables will be used. For the logistic regression analysis, postbaseline missing data will be imputed using the LOCF approach.

In addition, plots of changes from baseline in CDRS-R total score will be presented across study visits by treatment group.

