9.3 SELECTION OF STUDY POPULATION

9.3.1 Inclusion Criteria

Patients must provide assent to participate and their parent/guardian/LAR and caregiver (even if the same as the parent/guardian/LAR) must provide written informed consent prior to the conduct of any study-specific procedures (see also Section 5.3).

To be eligible to participate in the study, patients must meet the following criteria:

1. Male or female outpatients 7 to 17 years of age, inclusive, at Visit 1
2. Patients must meet DSM-5 criteria for MDD, confirmed by K-SADS-PL
3. Patients must have a score ≥ 40 on the Children's Depression Rating Scale-Revised (CDRS-R) at Visits 1 and 2
4. Patients must have a Clinical Global Impressions-Severity (CGI-S) score ≥ 4 at Visits 1 and 2
5. Patients must have a caregiver who can and is willing to consent to be responsible for safety monitoring of the patient, provide information about the patient's condition, oversee the administration of investigational product, and accompany the patient to all study visits (see Section 5.3)
6. Patients must have normal physical examination findings, vital sign values, clinical laboratory test results, and electrocardiogram (ECG) results or abnormal results that are judged not clinically significant by the Investigator
7. Female patients of childbearing potential must have a negative serum β -human chorionic gonadotropin (β -hCG) pregnancy test result at Visit 1
8. No known active COVID-19 infection. Subject must not have signs/symptoms associated with COVID-19 infection or known exposure to a confirmed case of COVID-19 infection during 14 days prior to Screening.

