9.5 EFFICACY AND SAFETY VARIABLES

9.5.1 Efficacy Assessments

The efficacy assessments will include the CDRS-R, CGI-S, and Clinician Global Impressions-Improvement (CGI-I). Efficacy assessments are not to be administered if the patient is not accompanied by his/her consented caregiver. The K-SADS-PL and all efficacy assessments will be conducted by experienced clinicians meeting training requirements and qualifications standards established by AGN and rater training vendor.

9.5.1.1 *Primary Efficacy Assessment*

The CDRS-R ([Appendix V](#); Poznanski and Mokros 1996) is a semi-structured, clinician-rated instrument designed for use with children and adolescents between the ages of 6-17 years and contains 17 ordinally-scaled items that evaluate the presence and severity of symptoms commonly associated with childhood depression. The CDRS-R total score ranges from 17 to 113.

The CDRS-R will be administered separately to the patient and to the caregiver. For each item, the clinician administering the interviews will select the rating that provides the best description of the patient and will then determine the total score.

9.5.1.2 *Secondary Efficacy Assessment*

The CGI-S ([Appendix VI](#); Guy 1976) is a clinician-rated scale used to rate the severity of the patient's current state of mental illness compared with an MDD patient population. The patient will be rated on a scale from 1 to 7, with 1 indicating a "normal, not at all ill" and 7 indicating "among the most extremely ill patients."

9.5.1.3 *Additional Efficacy Assessment*

The CGI-I is a clinician-rated instrument ([Appendix VII](#)). Based on the Investigator's clinical opinion, the total improvement or worsening of the patient's mental illness is rated on a scale from 1 to 7, with 1 being very much improved and 7 being very much worse, relative to Visit 2 (Baseline), regardless of whether the Investigator considers the worsening to be related to investigational product.

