The pattern for the pattern-mixture model will be defined by the patient's last visit with observed value. The observed CDRS-R total score at a visit is assumed to have a linear relationship with the patient's prior measurements. The dataset with missing values will be imputed under the assumption that the distribution of a missing observation differs from the observed only by a shift parameter value Δ . The dataset with missing values will be analyzed using the same model as the primary analysis for between-treatment group comparisons at Week 8. The imputation of missing values and the analysis will be performed multiple times and the inference of this sensitivity analysis will be based on the combined estimates using the standard multiple imputation technique. The values for Δ will be selected as 0 to 6 based on experience with historical data.

9.7.5.2 *Secondary Efficacy Parameter*

The secondary efficacy parameter is the change from baseline to the end of Week 8 in CGI-S score. This parameter will be analyzed similarly to the primary efficacy parameter.

A sensitivity analysis will also be performed using the LOCF approach as described in Section 9.7.5.1.

9.7.5.3 *Additional Efficacy Parameters*

The additional efficacy parameters will include the following at each postbaseline visit:

- CGI-I score
- Change from baseline in CGI-S score
- CDRS-R response ($\geq 40\%$ reduction in CDRS-R from baseline) rate
- CDRS-R remission ($\text{CDRS-R} \leq 28$) rate

CGI-I score and the change in CGI-S will be analyzed using the MMRM and LOCF approaches similar to those used for the primary efficacy parameter. For CGI-I score, the baseline CGI-S score will be used as the baseline variable.

The CDRS-R response rate and CDRS-R remission rate will be analyzed using a generalized linear mixed model (GLMM), based on logit link function, with random intercept and flexible terms of treatment group, visit, treatment-by-visit interaction, and baseline score. If the GLMM does not converge, a logistic regression model with treatment group and the baseline score as explanatory variables will be used. For the logistic regression analysis, the postbaseline missing data will be imputed using the LOCF approach.

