For the C-SSRS, the number and percentage of patients with suicidal ideation or suicidal behavior as recorded on the C-SSRS scale will be presented by treatment group. The distribution of responses for most severe suicidal ideation and suicidal behavior during the lifetime history, the double-blind treatment period and the down-taper period will also be presented by treatment group for the Safety Population. Supportive listings will be provided and will include the PID number, treatment group, visit number, lifetime history, and postbaseline values for each patient. Intensity of ideation, suicidal behavior type, and lethality of suicidal behavior will also be included in these listings.

9.7.6.5.2 *Growth Evaluation*

Weight and height will be presented as standardized z-scores adjusted for gender and age, using the lambda-mu-sigma method ([Cole TJ 1990](#)). To assess the impact of treatment on growth, the change from baseline in the age and gender adjusted height will be analyzed using an analysis of variance model with treatment as factor. A non-parametric (Wilcoxon) test will also be performed.

9.7.6.6 *Investigational Product Plasma Concentration Parameters*

Plasma samples will be analyzed for the concentrations of levomilnacipran using validated bioanalytical methods. Population PK parameters will be estimated using nonlinear mixed-effects modeling methods. The study will be prospectively powered to target a 95% confidence interval within 60% and 140% of the geometric mean estimates of clearance and volume of distribution for levomilnacipran ER, with at least 80% power.

9.7.7 *Health Economics and Outcomes Research Analyses*

Not applicable.

9.7.8 *Interim Analysis*

The interim analysis was conducted to identify early signs of futility after 62% of randomized patients had either completed or discontinued the study. The futility assessment of the primary efficacy parameter (CDRS-R total score) on ITT population was based on the conditional power as described in [Lan et al. 1999](#). In calculating the conditional power, it was assumed that the future patients to be enrolled into the Study will have similar efficacy as those of the existing patients of the same treatment group. The non-binding futility criteria was set when the conditional power for detecting a statistically significant treatment difference between the levomilnacipran treatment group

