4.0 INTRODUCTION

This statistical analysis plan (SAP) provides a more technical and detailed elaboration of the statistical analyses of the efficacy and safety data as outlined and specified in the protocol amendment #2 of Study LVM-MD-14 (dated 06 August 2020). Specifications of tables, figures, and data listings are contained in a separate document. The Modeling and Simulation Analysis Plan for pharmacokinetic will be prepared separately.

Study LVM-MD-14 is a Phase 3, multicenter, randomized, double-blind, placebo- and active-controlled, flexible-dose, parallel-group study in pediatric patients, ages 7-17 years, who have been diagnosed with major depressive disorder (MDD) using *Diagnostic and Statistical Manual of Mental Disorders*, 5th Edition (DSM-5) diagnostic criteria. The severity of MDD will be assessed based on Children's Depression Rating Scale – Revised (CDRS-R) scores, ranging in this study from 40 to 113.

The length of this study will be 10 weeks, including a 1-week screening/washout period, followed by an 8-week double-blind treatment period and a 1-week double-blind downtaper period. Signed informed consent from the patient or the patient's legally authorized representative and caregiver will be obtained before any study-related procedures are begun. All patients will be assigned a screening number. At the end of Visit 2 (Baseline), patients meeting the inclusion criteria will be randomized in 1:1:1 ratio to treatment groups of placebo, levomilnacipran, fluoxetine, respectively. A total of 480 patients (160 per treatment group) are planned to be randomized. Patients randomized to the levomilnacipran 40 – 80 mg/day group will receive 10 mg/day on Days 1-3, 20 mg/day on Days 4-7, and 40 mg/day during Weeks 2 through 8. Based on therapeutic response and tolerability, an additional dose increase to 80 mg/day is permitted at Week 3. During the down-taper period, patients will take levomilnacipran 40 mg/day for 2 days, and then levomilnacipran 20mg/day for 5 days. Patients randomized to the fluoxetine 20 mg/day group will receive fluoxetine 10 mg/day on Days 1-7, and then 20 mg/day during Weeks 2 through Week 8. During the down-taper period, patients will take fluoxetine 10 mg/day for 7 days. The dosing regimen and schedule for this study are presented in Table 4–1.

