16.2 DERIVED EFFICACY VARIABLES

If a patient misses a postbaseline visit or if his/her postbaseline visit is outside of the visit time window, a record for the scheduled visit will be imputed using the last observed nonmissing value immediately before the missing value. If the missing value occurs at Week 1, the baseline value will be carried forward for Week 1, provided that at least 1 subsequent postbaseline assessment is available. For a composite scale such as CDRS-R total score, individual items of the rating scale will not be carried forward. Only total scores will be carried forward using the LOCF approach.

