APPENDIX III. STATISTICAL ANALYSIS LIST FOR FUTILITY ANALYSIS

Table 20–2 List of Statistical Analysis for Futility Analysis

Table ID	Title	Analysis Population	
14.1-1.1	Disposition of Participants	Screened Population	
14.1-4.1.1A	Demographics	Safety Population	
14.1-4.1.3	Baseline Characteristics and Efficacy Variables	Intent-to-Treat Population	
14.2-1.1	CDRS-R Total Score: Summary of Baseline, Post-	Intent-to-Treat Population	
	baseline and Analysis of Change from Baseline - MMRM		
14.2-2.1	CGI-S Score: Summary of Baseline, Post-baseline	Intent-to-Treat Population	
11.2 2.1	and Analysis of Change from Baseline - MMRM	intent to Treat repairment	
14.3-1.1	Extent of Exposure	Safety Population	
14.3-2.1.A	Adverse Events: Overall Number (%) of	Safety Population	
	Participants with Adverse Events During the		
	Double-Blind Treatment Period		
14.3-2.2.A	Treatment-Emergent Adverse Events: Number (%)	Safety Population	
	of Participants with Treatment-Emergent Adverse		
	Events During the Double-Blind Treatment Period		
	by Treatment Group, System Organ Class and		
	Preferred Term		
14.3-2.3.A	Common (≥ 2%) Treatment-Emergent Adverse	Safety Population	
	Events: Number (%) of Participants by Preferred		
	Term During the Double-blind Treatment Period		
14.3-4.1	Laboratory Parameters: Number (%) of	Safety Population	
	Participants with Post-baseline Potentially		
	Clinically Significant Values During the Double-		
14251	blind Treatment Period	C.C. D. L.C.	
14.3-5.1	Vital Sign Parameters: Number (%) of Participants	Safety Population	
	with Post-baseline Potentially Clinically		
	Significant Values During the Double-blind Treatment Period		
14.3-6.1	ECG Parameters: Number (%) of Participants with	Safety Population	
14.3-0.1	Post-baseline Potentially Clinically Significant	Safety Population	
	Values		
14.3-7.2.A	C-SSRS: Number (%) of Patients with Suicidal	Safety Population	
17.J-1.2.A	Ideation or Suicidal Behavior During the Double-	Salety i opulation	
	blind Treatment Period		
* Table IDs are based on the Study SAP TFL shell document.			
Table 125 are based on the Study 571 112 shell document.			

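### Does the CDRS-R response rate need a stated rule on whether the scale minimum of 17 is subtracted?

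*SAP*

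**What the plan says.** SAP 10.3 (Additional Efficacy Parameters) defines "CDRS-R response (≥ 40% reduction in CDRS-R from baseline) rate" and, in the next bullet, remission as a CDRS-R of 28 or lower. Protocol 9.7.5.3 gives the same two definitions. Both rates are analysed at each postbaseline visit with a logistic mixed model that includes the baseline score. The fallback logistic regression includes it too.

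On the scale, Protocol 9.5.1.1 states: "The CDRS-R total score ranges from 17 to 113". On eligibility, Protocol 9.3.1 states: "Patients must have a score ≥ 40 on the Children's Depression Rating Scale-Revised (CDRS-R) at Visits 1 and 2". SAP 4.0 accordingly describes severity by CDRS-R "scores, ranging in this study from 40 to 113".

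SAP 16.2 (Derived Efficacy Variables) is where a percent-change formula might be expected. It deals only with carrying values forward: "Only total scores will be carried forward using the LOCF approach". SAP 4.0 adds that the specifications of tables, figures and listings are kept in a separate document, which is not among those reviewed.

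SAP 10.2 limits the fixed-sequence procedure to the primary parameter (CDRS-R change at Week 8) and the secondary one (CGI-S change at Week 8).

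**The concern.** A percent reduction is easiest to interpret on a scale that can reach zero. Here the floor is 17, and two computations are conceivable: (baseline − score)/baseline, or (baseline − score)/(baseline − 17). The plan does not print either.

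Two things look wrong at first. A patient who goes from 40 to 28 is in remission but has fallen by only 12/40 = 30%, so is not a responder. A reader who sees the two rates side by side may take that for an error. Also, on the raw total, the same 40% asks for a larger share of the attainable improvement from a patient with a low baseline than from one with a high baseline.

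At stake would be the reported response rate, if two programmers could properly follow the same text and reach different figures, or if the formula were chosen after unblinding.

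**Working it through.** **Inputs.** Scale range 17 to 113 (Protocol 9.5.1.1); lowest eligible baseline 40 (Protocol 9.3.1); response and remission rules (SAP 10.3).

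**The plan's own figure.** The item anchors in Protocol Appendix V reproduce the range. Minimum: 17 items × 1 = 17. Maximum: 14 items × 7 + 3 items × 5 (sleep, appetite, listless speech) = 98 + 15 = 113.

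**Where remission and response part on the raw total.** Response needs score ≤ 0.6 × baseline. Remission needs score ≤ 28.

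| Baseline | 0.6 × baseline | Scores that are remission but not response | Pairs |
|---|---|---|---|
| 40 | 24.0 | 25–28 | 4 |
| 41 | 24.6 | 25–28 | 4 |
| 42 | 25.2 | 26–28 | 3 |
| 43 | 25.8 | 26–28 | 3 |
| 44 | 26.4 | 27–28 | 2 |
| 45 | 27.0 | 28 | 1 |
| 46 | 27.6 | 28 | 1 |
| 47 and above | 28.2 or more | none | 0 |

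Total: 4 + 4 + 3 + 3 + 2 + 1 + 1 = 18 pairs.

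**With 17 subtracted.** Response needs score ≤ 17 + 0.6 × (baseline − 17). The cut-off is 17 + 0.6 × 23 = 30.8 at baseline 40 and rises from there. It always exceeds 28, so there are 0 such pairs.

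**Share of attainable improvement that a raw 40% requires**, 0.4 × baseline/(baseline − 17):
- baseline 40: 16/23 = 70%
- baseline 60: 24/43 = 56%
- baseline 113: 45.2/96 = 47%

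**How many patients, and how far apart the rates are (assumption-based).** The documents give a treatment difference of 4 and an SD of change of 11.1 (Protocol 9.7.9, SAP 14.0), but no baseline distribution and no placebo change. Assumed: normal baseline with mean 52, 56 or 60 and SD 8 or 9, truncated at 40; placebo change −12, −18 or −24; drug change 4 points larger; scores rounded and kept within 17 to 113.

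- Baselines of 40 to 46 make up about 4% to 20% of patients.
- Patients in remission but not response number fewer than 3 per arm of 160 in every scenario.
- At placebo −18, response is 30–39% (placebo) and 43–53% (drug) on the raw total. With 17 subtracted it is 53–63% and 66–75%. The two formulas differ by 21.7 to 23.3 points.

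Approximate power to separate drug from placebo on response, from a two-sided 5% two-proportion test with 160 per arm. This is simpler than the planned mixed model and ignores dropout.

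| Assumed placebo change | Raw total | 17 subtracted |
|---|---|---|
| −12 | 0.57–0.64 | 0.68–0.70 |
| −18 | 0.66–0.70 | 0.66–0.68 |
| −24 | 0.67–0.69 | 0.52–0.60 |

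Which formula separates the arms better depends on the placebo change. Neither is better throughout.

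**What the text means.** A 40% reduction in a score from baseline ordinarily means the change divided by the baseline value. The plan otherwise uses the raw total: the remission cut-off is a raw score, and the primary parameter is a raw change. No passage mentions a floor-adjusted score. Nor does any passage say that remission implies response; they are separate parameters, one relative and one absolute. Near the entry threshold of 40, two such rules can disagree without either being wrong.

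**The case for a change.** The strongest argument for a change is that one sentence costs almost nothing and would close off a choice that moves the reported rate by more than 20 points, and in some scenarios moves power as well. A formula left unwritten could in principle be picked with results in view. A supportive floor-adjusted rate would also make every remitter a responder.

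Part of this stands. No formula is printed in either document, and the power table shows that the two formulas cannot be called interchangeable. The case for leaving the plan alone therefore rests on the text having one plain reading. It does not rest on the choice being harmless.

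The rest does not carry. Writing the formula down would record what an analyst following SAP 10.3 would program anyway, and the separate table specifications may already contain it. A floor-adjusted rate would be a second definition of the same endpoint, added late. Protocol 9.7.8 reports: "The interim analysis was conducted to identify early signs of futility after 62% of randomized patients had either completed or discontinued the study". The interim outputs in SAP Appendix III ("STATISTICAL ANALYSIS LIST FOR FUTILITY ANALYSIS") include no response or remission table, so there is no sign that the definition was influenced. Even so, a second rate alongside the prespecified one would give readers two figures to choose between and would settle no question that the plan asks. The uneven share of attainable improvement comes with any unadjusted percent reduction on this scale. It applies equally to all arms, and baseline is in both models.

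**Conclusion.** No change is needed. The missing formula is a detail that analysts fill in one way: percent reduction of the raw total from baseline. The 18 remission-without-response pairs at baselines 40 to 46 are exact, but they come from pairing a relative rule with an absolute one and are not an inconsistency in the plan. Their expected size, fewer than 3 patients per arm of 160, rests on assumed baseline and change distributions. So do the gap between the formulas and the power figures. Whatever those distributions are, response remains an additional parameter outside the fixed sequence, and no primary or secondary conclusion depends on it.
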